Overview. The proposed study's primary aims are to examine the implementation and effectiveness and cost of computerized screening and BHS-delivered intervention. In context of the stepped wedge study design, HIV, SUD and depression outcomes will be compared between the intervention and observational phases. We will evaluate both short-term (i.e., within intervention phase) and long-term (i.e., within 1-2 years after initial intervention phase). As described in detail below, we will also employ two complementary study designs: 1) a repeated cross-section design with a different mix of individuals in each cluster (clinic) for examining implementation outcomes (e.g., Aim 1: screening rate) and 2) a cohort design for examining effectiveness in outcomes over time within the same individuals (e.g., Aim 2: retention in HIV care). Finally, we will evaluate implementation cost and cost-effectiveness, and perform qualitative interviews to assess provider- and clinic-level implementation barriers.

General Random Effects Model. Data analysis for both the cross-sectional and cohort approaches will use the random effects modeling framework which accounts for correlation between individuals within clusters and over time and is generalizable to non-normal distributions.¹¹ The general linear model is written as: $Y_{ijk} = m_{ij} + a_i + b_j + QX_{ij} + \epsilon_{ijk}$

where Y_{ijk} denotes the outcome for individual k in cluster i at time j . m_{ij} is the mean for cluster i at time j , a_i is the random effect for cluster i , β_j represent fixed effect corresponding to time j , and X_{ij} is the treatment mode in cluster i at time j . α_i and ϵ_{ijk} are independently distributed with appropriate distributions (e.g., logistic for binary outcomes, normal for continuous outcomes) and individual level covariates (e.g., gender, age, severity) to describe mean responses may be added to this model. The underlying distribution from the model can be linked to a linear predictor by appropriate transformations (e.g. binary outcome linearized using a logit link). These models may be estimated using SAS PROC MIXED or PROC NLMIXED for normal or non-normal distributions allowing for correlation between observations and variable cluster sizes.

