Aim 2. To examine the effectiveness of computerized screening and BHS-delivered intervention in HIV primary care among patients with moderate or high SUD risk or depression severity. We will first compare treatment initiation in specialty clinic for those with severe SUD or depression problems and anti-depression medication prescription rates, among all patients who screen positive (**Aim 2, Hypothesis 1**). The repeated cross-section analyses will be conducted using the random effects (mixed) model framework as above with the dependent variable (whether a patient received any prescription orders initiation with SUD specialty care or Psychiatry treatment for their SUD (depression) being dichotomous. Drawing from preliminary analyses, we will include all patient-level predictors (e.g. demographics such as age and gender, severity) that are likely to be related to these outcomes. These models will use logistic regression since the outcome is dichotomous. We will use the SAS® NL MIXED or similar procedure for analyses. Sample size permitting, we will also examine the use of Buprenorphine/Naloxone for the subset of HIV patients with opioid addiction.^{243,244}

We will also examine the longitudinal (cohort) effect of the intervention on clinical outcomes by comparing changes in HIV clinical parameters (**Aim 2, Hypothesis 2**) and SUD and depression severity (**Aim 2, Hypothesis 3**) for those who have return visits within the study observation period, adjusting for time between visits. We will examine changes in these values between the patient's initial screening and their subsequent visits using the random effects model described above. For example, we expect the coefficient of interest of the time x intervention variable to be positive, which would imply that BHS-delivered intervention results in greater increase in ART adherence.

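### Aim 2 Hypothesis 3 tests change in the scores that select its cohort, with no comparably selected observation-phase group, so regression to the mean can be read as an intervention effect

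*Protocol*

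**What the plan says.** All references are to the Protocol.

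- **Population.** The Aim 2 heading, in the opening list of aims and again under Data Analysis, limits the aim to effectiveness "among patients with moderate or high SUD risk or depression severity".
- **Outcomes.** The Aim 2 measures list TAPS risk level and PHQ-9, the two scores that the screening questionnaire produces.
- **Contrast.** Data Analysis, Aim 2 examines changes between the patient's "initial screening and their subsequent visits using the random effects model described above", among patients with return visits and with adjustment for the time between visits.
- **Interpretation.** The same paragraph opens with "We will also examine the longitudinal (cohort) effect of the intervention on clinical outcomes". Its example, on ART adherence, expects a positive time x intervention coefficient, "which would imply that BHS-delivered intervention results in greater increase in ART adherence".
- **Comparison.** The Data Analysis Overview states that "HIV, SUD and depression outcomes will be compared between the intervention and observational phases". In the list of aims, Hypotheses 1 and 2 of Aim 2 name the observation phase as comparator. Hypothesis 3 states only that symptoms fall after implementation.
- **Model.** In the General Random Effects Model, X_ij "is the treatment mode in cluster i at time j". The equation shows no interaction.
- **Data before implementation.** The observational-phase text says that screening for substances other than alcohol and tobacco was not standardised. Data Sources places the computerised results in the record only after implementation. The screening-measures and Modalities of Administration text says that the AOQ, which contains the PHQ-9, was already in routine use in the health system.

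**The concern.** Patients chosen because a score is high will, on average, score lower next time, because part of the first score is transient variation or measurement error. Here the selecting score is also the baseline of the change score. Only a comparison group selected in the same way shows how much of the fall would have happened anyway, and the protocol describes none.

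Two results are at stake. The first is the symptom finding of Aim 2, which would be reported as effectiveness. The second is Aim 3. Its opening statement extends cost-effectiveness to each SUD and depression outcome, and its analysis section defines the ratio between the observation and intervention phases. A fall produced by selection could enter that ratio as a gain.

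**Working it through.** The protocol gives no effect size, SD, retest correlation or positive-screen rate for Hypothesis 3, so there is no stated figure to reproduce. The numbers below rest on assumed inputs and show scale only.

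**1. Patients who enter on PHQ-9.** Assumed: mean 5, SD 5 to 5.5, cut 10, retest correlation r 0.6 to 0.85, bivariate normal, no treatment effect. With z = (10 − 5)/SD,

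expected fall = (1 − r) × SD × φ(z) / (1 − Φ(z)).

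- SD 5: z = 1, φ/(1 − Φ) = 0.2420/0.1587 = 1.525, so the group starts 7.63 points above the mean. Falls: 0.15 × 7.63 = 1.14 (r 0.85); 0.30 × 7.63 = 2.29 (r 0.7); 0.40 × 7.63 = 3.05 (r 0.6).
- SD 5.5: the group starts 7.99 points above the mean. Falls: 1.20 (r 0.85) and 3.20 (r 0.6).

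**2. Whole cohort (PHQ-9 or SUD).** Let p be the share above the PHQ-9 cut and s the share at SUD risk (assumed 15 to 30%). If the two are independent,

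expected fall = (1 − r) × SD × φ(z) × (1 − s) / (p + s(1 − p)).

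- SD 5, r 0.85, s 30%: 0.15 × 5 × 0.2420 × 0.70 / 0.4111 = 0.31.
- SD 5, r 0.7, s 15%: 0.30 × 5 × 0.2420 × 0.85 / 0.2849 = 1.08.
- SD 5.5, r 0.6, s 15%, correlation 0.3 between SUD risk and PHQ-9 (simulated): about 2.0.

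**3. What the test would do.** A null simulation used 4,600 patients (the protocol's figure) and assumed 70% returning, 10 to 30% above the cut and r 0.5 to 0.9.

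| Contrast | Null difference (SD) | Rejection |
|---|---|---|
| Before-after in the selected group | −0.12 to −0.88 | 100% |
| Against unselected observation-phase patients | −0.12 to −0.88 | 100% |
| Against observation-phase patients selected by the same cut-off | about 0 | 3.9 to 6.3% (nominal 5%) |

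So a phase comparison helps only if both phases are selected alike.

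**4. The time x intervention term.**

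- *Intervention means phase (X_ij).* If every score comes from Phase 2, X = 1 throughout. The columns 1 and X coincide, as do time and time x X. The design has rank 2 of 4, so the interaction cannot be estimated and only the before-after slope remains.
- *Intervention means a patient's receipt of behavioral health specialist (BHS) care.* The interaction can be estimated, but Aim 1 Hypothesis 3 expects receipt to rise with severity. Receipt rates were assumed for PHQ-9 below 10, 10 to 14, and 15 or more. At 30/40/50% to 20/40/60% the null interaction is about −0.2 to −1.2 points; at 40/40/60% it is about −0.1 to −0.3. The protocol allows that "individual level covariates (e.g., gender, age, severity) to describe mean responses may be added to this model", but severity added only as a main effect leaves it at −0.15 to −1.22. Adjusting change for the baseline score brings it to within about 0.03 of zero.

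**5. All repeat completers, whatever the first score.** The null fall is 0.00 if repeating is unrelated to the first score. It is 0.04 to 0.12 if 60% repeat above the cut against 50% below, and 0.08 to 0.27 if 75% against 50%.

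No size is offered for TAPS. It is scored per substance, and its 12-month look-back overlaps when screening is repeated at 6 months.

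**The case against.** **A PHQ-9 comparator may exist.** The AOQ was already standard care, and depression data are extracted for the observation phase. A reader might infer from the TAPS gap that no symptom outcome can be compared across phases, so that all of Hypothesis 3 must be demoted. The documents do not support that. What they lack is a rule that identifies observation-phase patients with moderate or high scores and fixes their initial score, and any statement of coverage in the three clinics. This objection stands, and it changes the remedy for PHQ-9.

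**The intervention term is not undefined.** X_ij is defined, Data Analysis, Aim 1 uses a phase indicator, and Aim 3 uses the name of the BHS-delivered intervention at phase level. The time x intervention sentence is an example about ART adherence, which does not select the cohort. This largely stands: phase is the better-supported reading, and receipt is only a possible one. The example still matters because the same paragraph applies the same model to Hypothesis 3. Non-estimability is conditional on all scores coming from Phase 2, since provider-documented screening in the observation phase also counts as screening.

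**The Aim 3 link is partly inferred.** The only worked ratio uses ART adherence, and SUD and depression outcomes may also mean treatment initiation or prescribing. That is fair, but the opening Aim 3 statement covers each such outcome and excludes neither score.

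**The equation shows no patient-level random effect.** A reader might infer that repeated measures are treated as independent. The text says that the framework "accounts for correlation between individuals within clusters and over time and is generalizable to non-normal distributions", and the exact random-effects structure is a matter for the statistical analysis plan. No point is made of it.

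**The sizes are assumed.** This is correct. A normal distribution with mean 5 and SD 5 even puts about 16% of scores below zero. The direction does not depend on these inputs.

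**Hypothesis 3 is worded only as a decrease.** That is close to an uncontrolled claim, but the analysis section calls the result an effect and the Overview promises a phase comparison.

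**Conclusion.** The concern holds for the selection, the contrast and the interpretation, all of which the protocol itself fixes. Followed as written, the plan yields an apparent symptom decrease with no treatment effect, and nothing in it separates that fall from benefit. For TAPS no baseline before implementation is described. For PHQ-9 a fair comparison may be possible but is not specified.

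The direction is supported by the documents. The size, roughly 1 to 3 PHQ-9 points in those who enter on PHQ-9 and 0.3 to 2 points over the whole cohort, is illustrative and rests on an assumed distribution, cut, retest correlation and SUD share. The receipt figures apply only if BHS receipt is what is analysed. This should be fixed; confidence is medium.

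**What to change.** 1. **PHQ-9.** Where observation-phase scores exist, compare change with observation-phase patients selected by the same cut-off on the same score. State that PHQ-9 administration in usual care may have been selective.
2. **TAPS, and PHQ-9 if coverage is inadequate.** Report Hypothesis 3 as uncontrolled within-phase change in a score-selected group, not as an intervention effect. Do not enter that change into any Aim 3 ratio as a phase difference.
3. **Supporting analysis.** Analyse all patients with two or more TAPS/AOQ completions, whatever the first score. State that repeat completion is selective (it is voluntary, and clinicians may re-administer as follow-up), so this reduces the artefact but may not remove it.
4. **Interaction.** State that intervention in time x intervention means phase. If BHS receipt is analysed instead, adjust change for the baseline score (baseline x time, or follow-up score with baseline as covariate) and label it a non-randomised comparison.

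The cost is analysis wording, a check of PHQ-9 coverage before implementation, and additional analyses of record data in the same software. The downside is that the symptom result becomes smaller or non-comparative, and Aim 3 may lose some symptom-based ratios.

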**TITLE:**

Computerized Substance Use and Depression Screening and Behavioral Treatment in HIV Primary Care

NCT NUMBER:

NCT03217058

VERSION DATE:

October 5, 2022

Research Question: What are the key barriers to implementation, factors associated with effectiveness, and cost of tablet-based screening for the continuum of SUD severity and depression, followed by BHS-delivered interventions for those who screen positive.

Aim 1. To evaluate the implementation of computerized SUD and depression screening and BHS-delivered intervention in HIV primary care.

Hypothesis 1: SUD and depression screening rates and BHS-delivered intervention will be higher in the intervention phase compared with the observation phase and will be maintained long-term.

Hypothesis 2: Greater HIV severity and younger age will increase screening rates for SUD and depression.

Hypothesis 3: More BHS-delivered intervention will occur with higher HIV, SUD and/or depression severity.

Aim 2. To examine the effectiveness of computerized screening and BHS-delivered intervention in HIV primary care among patients with moderate or high SUD risk or depression severity.

Hypothesis 1: SUD and/or psychiatry specialty care treatment initiation and antidepressant prescription use will be greater in the intervention phase compared with the observation phase.

Hypothesis 2: HIV outcomes, including ART adherence, HIV RNA control, VACS index score, and retention in HIV care will be improved in the intervention phase compared with observation phase.

Hypothesis 3: SUD and depression symptoms will decrease after implementation of the intervention.

Aim 3. To determine implementation costs and cost-effectiveness of screening and BHS-delivered intervention.

We will measure the cost per patient screened, and among those screening positive, the cost per patient initiating BHS-delivered intervention. We will also evaluate the cost-effectiveness of the intervention for achieving improvements in each HIV, SUD and depression outcome.

Aim 4: Perform key informant interviews to evaluate provider- and clinic-level implementation barriers and facilitators to computerized screening and BHS-delivered intervention.

Semi-structured interviews for selected providers and clinic staff, including qualitative and quantitative components, will be performed in each clinic.

Study Design

Description of Study Phases

Phase 1: Data only

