- **SUD and depression treatment initiation.** Patients scoring in the high SUD risk level on the TAPS or moderate to severe depression on the PHQ-9 will be encouraged to initiate specialty SUD or psychiatry treatment, and the BHS will use MI to help enhance motivation to initiate care. We will analyze SUD and depression treatment initiation rates using electronic administrative data; that is, whether the patient attended at least one in-person or phone visit with a BHS and/or in SUD or psychiatry treatment.
- **Antidepressant prescription rates.** Any prescription for antidepressants, including standard medications based on best practices guidelines in the treatment of depression.^{211,230}
- **Antiretroviral (ART) medication adherence.** ART adherence will be defined using the Medication Possession Ratio (MPR)^{234,235} for each ART prescribed.²³⁶ MPR is calculated using a numerator of days' supply dispensed from first fill to end of the interval (i.e., 12 months), and a denominator of total days between first fill to end of the interval, with values ranging from 0% to 100%. Mean refill adherence will be calculated across all individual ARTs dispensed in the interval²³⁷ distinguishing between true non-adherence or a change in ART (i.e., a new ART medication prescribed within 30 days) as in our previous work.^{238 179}
- **HIV RNA response.** HIV RNA control, defined as undetectable HIV RNA levels below 75 copies/ml.
- **Retention in care.** We will use the Institute of Medicine's encounter-based definition of retention, defined as ≥ 2 HIV primary care visits within a 12-month period, ≥ 90 days apart.¹⁵⁵
- **VACS index score.** The VACS score has been shown to correlate with mortality.¹⁸⁶ It incorporates 7 routinely collected clinical variables, including age, CD4, HIV RNA, hemoglobin, fibrosis index 4 (FIB-4), Hepatitis C, and

estimated glomerular filtration rate. The FIB-4 index incorporates age, platelets, and two liver function test results, including aspartate aminotransferase and alanine aminotransferase.

- **TAPS (SUD risk level) and PHQ-9 (Depression).** See section **C.6.b.**

Data Analysis

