Aim 3. To determine implementation costs and cost-effectiveness of screening and BHS-delivered intervention. Costs will be obtained as described in **C.8.c.** We will assess the incremental cost-effectiveness ratio as the additional cost per unit of outcome (e.g., 1% increase in mean ART adherence) between the observation and intervention phases. For example, if the BHS-delivered intervention costs \$100 more per patient than during the observational phase and increases mean ART adherence from 85% to 90%, then the intervention costs \$2000 per additional unit of adherence. A cost-effectiveness acceptability curve will be obtained from the distribution of the ICER which will be constructed using the bootstrap method based on the variances of estimates of costs and effectiveness as we have done in prior work.¹⁶⁶ This can be used by policy-makers to determine potential gain in effectiveness for acceptable cost thresholds.

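### Aim 3's worked cost-effectiveness example gives 2000 dollars per unit of adherence, but per the 1% unit named one sentence earlier it is 20 dollars; 2000 holds only per 100 percentage points

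*Protocol*

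**What the plan says.** Protocol, Data Analysis, Aim 3, defines the ICER between the observation and intervention phases as the "additional cost per unit of outcome (e.g., 1% increase in mean ART adherence". The following sentence is a hypothetical: the intervention costs 100 dollars more per patient and "increases mean ART adherence from 85% to 90%, then the intervention costs" 2000 dollars "per additional unit of adherence". The size of that unit is not restated.

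Under Aim 2 measures, ART adherence is the Medication Possession Ratio (MPR), days' supply dispensed divided by days in the interval, "with values ranging from 0% to 100" percent.

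On uncertainty, the Aim 3 analysis text says: "A cost-effectiveness acceptability curve will be obtained from the distribution of the ICER". That distribution comes from a bootstrap, with a reference to prior work, and policy-makers are to read the curve against acceptable cost thresholds. The opening statement of Aim 3 extends cost-effectiveness beyond adherence, "for achieving improvements in each HIV, SUD and depression outcome".

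**The concern.** A worked example normally shows how the definition just given is to be applied. Here the definition and the example concern the same outcome, mean ART adherence, yet the printed result does not follow from the unit just named.

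What is at stake is how the Aim 3 results are read. The ratio and the acceptability curve mean something only against a threshold, and a threshold has a unit. Someone who takes the definition at its word will think in dollars per percentage point; someone who copies the example will compute dollars per 1.0. A percentage measure such as MPR also stands beside a yes/no outcome, "HIV RNA control, defined as undetectable HIV RNA levels below 75 copies/ml", for which 1.0 (one more patient with control) is a natural unit, so both scales could plausibly appear in the same report.

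A second, smaller matter is the curve. Taken literally, a curve read off the distribution of the ratio goes wrong once some bootstrap replicates show a negative effect, because a negative ratio can mean either a very good or a very bad result.

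**Working it through.** **Inputs.** Incremental cost 100 dollars per patient; mean adherence 85% and 90%; example unit a 1% increase; printed result 2000 dollars per unit (all Protocol, Data Analysis, Aim 3). MPR scale 0% to 100% (Protocol, Aim 2 measures).

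**Formula.** ICER = incremental cost / incremental effect.

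**Reproducing the printed figure.** With adherence as a proportion: 100 / (0.90 − 0.85) = 100 / 0.05 = 2000 dollars per 1.0. This is a coherent rate: 20 patients at 100 dollars cost 2000 dollars and together gain 20 × 0.05 = 1.0.

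**With the unit that the protocol names.**
- Per percentage point: 100 / (90 − 85) = 100 / 5 = 20 dollars.
- Per 1% relative increase, the other reading of 1%: 5/85 = 5.88%, and 100 / 5.88 = 17 dollars.

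Neither gives 2000. For 2000 dollars per percentage point to be true, the added cost would have to be 2000 × 5 = 10,000 dollars, or the gain 100/2000 = 0.05 percentage points.

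**Size of the mismatch.** 2000 / 20 = 100.

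**What a misread threshold does.** Take a threshold of 20 per unit, at which the example just breaks even in percentage points: 20 × 5 − 100 = 0 dollars net benefit. Apply the same 20 to the effect as a proportion: 20 × 0.05 − 100 = −99 dollars. Only the unit has changed.

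**The acceptability curve.** Two replicates made by changing signs in the protocol's example show the difficulty:
- costlier and worse: cost +100, effect −5, ratio −20; net benefit at threshold 20 is 20 × (−5) − 100 = −200;
- cheaper and better: cost −100, effect +5, ratio −20; net benefit is 20 × 5 + 100 = +200.

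The ratios are identical and the conclusions opposite. Counting ratios below the threshold accepts both.

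How much this matters depends on standard errors (SEs), which the protocol does not give. The following is illustration only. **Assumptions:** effect normal with mean 5 points, cost normal with mean 100 dollars, independent, threshold 20 dollars per point. The share of ratios below 20 is P(C < 20E, E > 0) + P(C > 20E, E < 0). The net-benefit share is P(20E − C > 0), which is 50.0% in every row because the means break even.

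| Assumed effect SE | Assumed cost SE | Share of ratios below 20 | Net-benefit share |
|---|---|---|---|
| 1 | 30 | 50.0% | 50.0% |
| 2.5 | 15 | 52.3% | 50.0% |
| 2.5 | 30 | 52.3% | 50.0% |
| 2.5 | 60 | 52.1% | 50.0% |
| 5 | 30 | 65.9% | 50.0% |

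The gap is close to the probability that the effect is below zero (2.28% at effect SE 2.5) and vanishes when the effect is clearly positive.

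**The case against.** **It is not a wrong division.** This stands. 100/0.05 is 2000, and MPR is by construction a proportion, with percent only its notation. A reader might infer that the protocol's arithmetic is faulty; it is not. The defect is that the result is on a different scale from the unit announced for the same outcome, and nothing in the text says so. That the 1% is offered only as an example does not reconcile the two sentences.

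**Nothing depends on it.** Largely true. The sentence is hypothetical, no cost threshold is printed, and no test, sample size or planned estimate uses the 2000. A reader might infer that the Aim 3 results themselves will be off by 100; the documents do not support that. The risk lies in how ratios and thresholds are later scaled and read.

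**The curve criticism supplies its own faulty method.** Partly true. The protocol does not say that negative ratios will be counted as cost-effective, and the prior work it cites is not available here, so it would be wrong to claim that the curve will be miscomputed. What remains is that the text names the ratio's distribution as the source of the curve, and that distribution alone cannot support it once effects cross zero.

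**Direction of improvement and a unit for every outcome.** A reader might also object that the protocol does not fix which sign counts as better. That is not a defect: Aim 3 speaks of improvements, and Aim 2, Hypothesis 3 states that "SUD and depression symptoms will decrease after implementation of the intervention". Coding the direction and listing a unit for each outcome are details that a statistical analysis plan may hold.

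**Conclusion.** The unit inconsistency is certain and can be checked from two consecutive sentences: 20 dollars per percentage point against a printed 2000, a factor of 100. It rests on no assumption beyond reading 1% as one percentage point; the relative reading gives 17 dollars and does not help. Its practical weight is modest, because the example is illustrative, but it is the only worked definition of the ratio for a whole study aim and should be corrected.

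The curve point is secondary and conditional. It applies only to outcomes whose bootstrap effect replicates cross zero, and only if the ratio's distribution is used literally. In the illustration the overstatement runs from none (effect SE 1) to 15.9 percentage points (effect SE 5, as large as the effect itself). Those SEs are assumed, so the figures show the mechanism and do not predict this study's results.

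**What to change.** 1. In Data Analysis, Aim 3, either change the result to 20 dollars per 1-percentage-point increase in mean ART adherence, or keep 2000 dollars and state that it is per 1.0 on the 0-1 scale, that is, 100 percentage points. In the second case, bring the example unit in the preceding sentence into line.
2. Express cost thresholds for adherence in the same unit.
3. Define the acceptability curve, at each threshold, as the share of bootstrap replicates with threshold × effect − cost above 0, with cost and effect taken as a pair from the same replicate.

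The first two are wording changes. The third is one sentence and a few lines of code, and needs no additional data.
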